8.4 Study Population with inclusion and exclusion criteria

For the incidence and prevalence estimations, the complete database population will be included.

For disease duration, all patients with the diagnosis of interest will be included, without any exclusion criteria.

Inclusion criteria are described in Table 5.

Criterion	Details	Assessment window	Care Settings ¹	Code Type	Applied to study populations:
Patients with a disease diagnosis	Earliest recording of disease diagnosis will be identified, this can be before or during observation time	Complete history and observation period of patient	PC, IP and OP	SNOMED code	Patients with disease diagnosis
Pediatric patients	Earliest recording of disease is at age 0-17	Complete history and observation period of patient	PC, IP and OP	SNOMED code	Patients with disease diagnosis at paediatric age
Adult patients	Earliest recording of disease is at age 18+	Complete history and observation period of patient	PC, IP and OP	SNOMED code	Patients with disease diagnosis at adult age

¹IP = inpatient, OP = outpatient, NA = not applicable, PC = primary care

No exclusion criteria are applied

8.5 Variables

8.6.1. Exposure/s (where relevant)

No exposures are considered in this study.

[figure not shown]
8.6.2. Outcome/s (where relevant)

While the diseases in this study are all chronic, for each disease, only the first occurrence of the diagnosis will be selected. Details are provided in Table 6. The codes (concept ids) used for selection of the diagnoses are listed in Appendix I - Concept definitions. As well as the occurrence of disease mortality is also an outcome.

Table 6. Operational Definitions of Outcome.

Outcome name	Details	Type of outcome	Washout window	Care Settings ¹	Code Type	Applied to study populations
Cystic fibrosis	Preliminary code list provided in Table 1 in Appendix I	Incidence and prevalence	[-Inf, -1]	PC, IP and OP	SNOMED	Total population
Haemophilia	Preliminary code list provided in Table 1 in Appendix I	Incidence and prevalence	[-Inf, -1]	PC, IP and OP	SNOMED	Total population
Pulmonary arterial hypertension	Preliminary code list provided in Table 1 in Appendix I	Incidence and prevalence	[-Inf, -1]	PC, IP and OP	SNOMED	Total population
Pancreatic cancer	Preliminary code list provided in Table 1 in Appendix I	Incidence and prevalence	[-Inf, -1]	PC, IP and OP	SNOMED	Total population
Sickle cell disease	Preliminary code list provided in Table 1 in Appendix I	Incidence and prevalence	[-Inf, -1]	PC, IP and OP	SNOMED	Total population
Mortality		Time-to-event				Patients with disease

¹IP = inpatient, OP = outpatient, PC = primary care

8.6.3. Other covariates, including confounders, effect modifiers and other variables (where relevant)

For all diseases, next to a cohort including all diagnosed patients, a paediatric (age 0-17) and an adult (age 18 and older) cohort will be generated. To generate these two cohorts, age at first diagnosis will be calculated.

8.6 Study size

No sample size has been calculated.

8.7 Analysis

The analyses which will be done are given in **Table 7**. Details are provided in Sections 8.8.3 – 8.8.6.

Table 7. Description of Study Types and Type of analysis.

STUDY TYPE	STUDY CLASSIFICATION	TYPE OF ANALYSIS
Population-level descriptive epidemiology	Off-the-shelf	 Incidence rates of the condition of interest Prevalence rates of the condition of interest
Patient-level characterisation	Off-the-shelf	- Survival time

Analyses will be done and reported in each database separately. A meta-analysis of results will be carried out, which is described in section 8.9.

8.8.1. Outcome cohorts

The outcome cohorts for the diseases will include only the first diagnosis date of each patient. This diagnosis date is cohort start date. Cohort end date is the end of the observation period of the patient.

Based on birth date of the patient and date of first diagnosis, age at diagnosis will be determined. Age will be categorized into 0 - 17 year (paediatric) and 18 year and older (adult). For each disease, if feasible, three outcome cohorts will be generated:

- patients with first diagnosis at any age •
- patients with first diagnosis at paediatric age
- patients with first diagnosis at adult age

All analyses described below will be done for each of these cohorts, under restriction of the minimum cell count criterion, i.e. for outcome cohorts with less than 5 subjects no analyses will be done.

8.8.2. Descriptive statistics

An attrition table will be given to report the number of subjects used in the analysis.

For the disease cohorts, sex and age at diagnosis will be described.

D2.2.3 - Study Protocol for P2-C1-013				
Author(s): [name], [name]	Version: 2.0			
	Dissemination level: Public			

8.8.3. Point prevalence

The R package *IncidencePrevalence* will be used to estimate complete point prevalence.

Point prevalence will be estimated for January 1 of each calendar year during the study period. Denominator is the total number of persons in observation at the specific time point. All persons with a diagnosis before the time point and in observation in the database at this time point contribute to the numerator. Point prevalences will be plotted against calendar year. The point prevalence at 01/01/2016 will be used for the comparison with the indirect estimated prevalence.

In **Figure 1** some patients are shown with their observation period and time of first diagnosis relative to the study period. The observation period of patient 1 includes the time point for the point prevalence at 01/01/2016. Therefore, this patient contributes to the denominator for the point prevalence. First diagnosis of this patient is before 01/01/2016 (and even before the study period and before the patient's observation period), so this patient also contributes to the numerator. Likewise, patient 2 is in observation at 01/01/2016 and is diagnosed before, so this patient also contributes to both the denominator and numerator. For patient 3, 01/01/2016 falls within the observation period and therefore this patient contributes to the denominator only. The date of first diagnosis for patient 3 is after 01/01/2016, so this patient does not contribute to the numerator for point prevalence. The observation period of patient 4 ends before 01/01/2016. Hence this patient does not contribute to the denominator nor the numerator.

The estimate of the point prevalence will be reported with 95% confidence intervals (CI) using Wilson score method.

[figure not shown]

Figure 1 Diagram with patient data to illustrate incidence and prevalence calculations.

Dissemination level: Public

While the complete point prevalence estimated at the mid-point of the study period (January 1st 2016) will be used to compare with the indirect estimate of prevalence, estimates of complete point prevalence on January 1st of every year of the study period will also be reported to describe potential trends over time.

8.8.4. Incidence rates

Incidence rates will be estimated over the complete study period and by calendar year. Denominator is the total number of person-years at risk, i.e. observation time of a person within the study period, until a diagnosis occurs or observation time ends. To the numerator, only first diagnoses within the observation time of a patient (and within study period or in the respective calendar year) will contribute. The incidence rate by calendar year will be plotted to check stability over time. This will be used in the discussion about the validity of the indirect estimated prevalence.

Patient 1 in **Figure 1** is diagnosed before the study period. Therefore, this patient is not at risk for incident disease during the study period, so s/he does not contribute with person time to the denominator for the incidence rate (i.e. patients with a diagnosis before the start of follow-up will be excluded from the analysis for incidence). Therefore, the diagnosis also does not contribute to the numerator. Patient 2 contributes person time from start of observation period to the time of diagnosis. This diagnosis, within the study period and within the observation period of the patient, contributes to the numerator. Both patient 3 and patient 4 contribute person time from start of study period to time of diagnosis, and again their diagnoses contribute to the numerator.

The estimate of the incidence rate will be reported with 95% CI using exact Poisson method.

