8.3 Follow-up

For all individuals in the databases, the observation period is recorded, i.e. the period during which the individual is monitored. In the primary care databases used in this study, it is the period the individual is registered in the GP practice.

• For the incidence estimation, the follow-up is the part of patient's observation period that overlaps with the study period. Only first diagnoses which fall within this follow-up period will contribute to

the incidence numerator. The follow-up period will contribute time at risk to the person-years denominator, restricted to the time before the first diagnosis of the relevant disease, if present.

- For the direct estimation of the point prevalence, a disease diagnosed before an individual's observation period, if present, will also be captured. Diagnoses before the observation period can be present if a GP has received information about the patient's history from the former GP, or if a GP enters historical information, e.g. the diagnosis date of an inherited disease. However, individuals can only contribute to the point prevalence numerator and denominator if the time point used to assess the point prevalence is within their observation period.
- In the survival analysis, the follow-up of patients starts at the first diagnosis of the disease of interest and ends at patient's death, end of patient's observation period or end of the study period, whatever comes first.

Further information on follow-up time is given in Table 4.

	D2.2.3 - Study Protocol for P2-C1-013			
EUM	Author(s): [name], [name]	Version: 2.0		
		Dissemination level: Public		

Table 4. Operational Definition of Time 0 (index date) and other primary time anchors.

Study population name(s)	Time Anchor Description	Number of entries	Type of entry	Washout window	Care Setting ¹	Code Type ²	Incident with respect to
Total population	Start of FU: latest of: - entry in database - start of study period (01/01/2010) End of FU: earliest of: - date of mortality - end of patient's observation period, i.e. deregistration of patient or end of GP data contribution - end of study period (31/12/2022)	1	NA	NA	PC, IP and OP	NA	NA

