11 LIMITATIONS OF THE RESEARCH METHODS

The study will be informed by routinely collected healthcare data and so data quality issues must be considered. Also, the period during which information about the patient is present will often be limited because it might be restricted to the period the patient is registered in the GP practice and to the period the GP data is made available for the database. A GP can have entered historical events, for example the diagnosis of an inherited disease, and/or information received from a patient's former GP might be imported. However, this is not standard practice for all GPs.

This means diagnoses might be missing if falling outside the monitored period. It can also be the case that the first recorded diagnosis of the disease is not the correct date of onset. For example, this can be the case

Version: 2.0

Dissemination level: Public

when the first diagnosis was before the patient's observation period in the database. Also, there might be patients with asymptomatic disease, which results in a late diagnosis, sometimes only shortly before death. These incorrect dates of diagnosis can give bias in the estimation of incidence and prevalence, especially in the estimation of the median disease duration. Moreover, a missing first diagnosis might result in an incorrect classification of the disease being diagnosed at adult age, while it should be paediatric. However, this would not affect the comparison between direct and indirect estimation methods.

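### Incidence time at risk starts at database entry with no prior-observation requirement, so disease diagnosed before registration but first coded afterwards counts as incident and inflates the indirect prevalence

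*Protocol*

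**What the plan says.** - **Start of time at risk.** For the total population, Table 4 (Section 8.3) gives "Start of FU: latest of: - entry in database" or the start of the study period, 01/01/2010. The washout for this population is NA.
- **Observation period.** Section 8.3 defines it for these databases: "it is the period the individual is registered in the GP practice".
- **Incidence numerator.** Section 8.8.4 counts "only first diagnoses within the observation time of a patient". Its worked example confirms that there is no lead-in: "Patient 2 contributes person time from start of observation period to the time of diagnosis".
- **Protection against existing cases.** Section 8.8.4 states that "patients with a diagnosis before the start of follow-up will be excluded from the analysis for incidence", and Table 6 sets the outcome washout to [-Inf, -1]. Both act only on what is recorded.
- **Completeness of history.** Section 11 says that entering or importing history is not routine for every GP, and adds: "It can also be the case that the first recorded diagnosis of the disease is not the correct date of onset". It accepts that wrong dates can bias incidence, prevalence and above all median duration. It then turns to paediatric cases misclassified as adult, and ends: "However, this would not affect the comparison between direct and indirect estimation methods".
- **Use of the estimates.** Direct prevalence (8.8.3) needs only a diagnosis before 01/01/2016 in a person under observation on that date. Indirect prevalence (8.8.6) is I x D.

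**The concern.** A patient with long-standing disease who joins a practice without an imported history looks disease-free at entry. When the GP codes the disease, the patient becomes an incident case. The diagnosis date hardly matters for direct prevalence, provided it falls before 01/01/2016, but it decides whether the patient enters I.

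The study exists to compare the two prevalence estimates. This error falls mainly on one of them, and by an amount that grows with disease duration. A gap produced by registration turnover could be read as failure of the indirect method in the lifelong inherited diseases, while pancreatic cancer would show almost none of it.

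**Working it through.** The protocol states no expected rate, turnover or completeness of history, so there is no figure to reproduce. All inputs below are assumptions:

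- D, mean disease duration: 1, 5, 20, 40 years
- T, mean length of registration: 10 years (range 5-20)
- f, share of already diagnosed new registrants whose history is not entered: 10-50%
- lag from registration to first coding: mean 0.5 year (range 0.25-2)

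**Step 1: incidence.** For a rare disease in steady state, existing cases number I x D per person. With arrivals balancing departures, they register at rate 1/T. A share f arrives without history, and a fraction q of these is coded before leaving or dying:

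q = (1/lag) / (1/lag + 1/T + 1/D)

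I_obs / I_true = 1 + f x (D/T) x q

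Example, D = 20, f = 25%: q = 2/(2 + 0.1 + 0.05) = 0.930, and 1 + 0.25 x 2 x 0.930 = 1.47.

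| D (years) | q | f = 10% | f = 25% | f = 50% |
|---|---|---|---|---|
| 1 | 0.645 | 1.01 | 1.02 | 1.03 |
| 5 | 0.870 | 1.04 | 1.11 | 1.22 |
| 20 | 0.930 | 1.19 | 1.47 | 1.93 |
| 40 | 0.941 | 1.38 | 1.94 | 2.88 |

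With T from 20 down to 5 years at f = 25%, the factor is 1.24-1.89 for D = 20 and 1.48-2.80 for D = 40.

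**Step 2: direct prevalence.** A simulation of the protocol's rules (13-year study period, prevalence at year 6, T = 10) gave the same incidence factors to within 0.02. All-ages direct prevalence stayed at 0.98-1.00 of its true value with a 0.5-year lag. With a 2-year lag and f = 50% it fell to 0.92.

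**Step 3: does a shorter D cancel the inflated I?** The same simulation, f = 0 to f = 50%:

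| D, survival shape | I factor | Median as in 8.8.5 | Indirect/direct | Median with delayed entry | Indirect/direct |
|---|---|---|---|---|---|
| 1, exponential | 1.00 to 1.03 | 0.79 to 0.77 | 0.79 to 0.83 | 0.68 to 0.69 | 0.68 to 0.75 |
| 5, exponential | 1.00 to 1.20 | 6.55 to 5.36 | 1.29 to 1.33 | 3.46 to 3.45 | 0.68 to 0.86 |
| 20, exponential | 1.01 to 1.93 | 63.1 to 49.2 | 3.19 to 4.85 | 13.9 to 13.8 | 0.70 to 1.36 |
| 40, Weibull shape 3 | 1.00 to 2.90 | 56.9 to 54.4 | 1.43 to 4.03 | 39.6 to 32.7 | 0.99 to 2.42 |

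The change across f is what matters here. The ratios at f = 0 differ from 1 because of separate features (survival time counted before observation, median in place of mean). Under 8.8.5 as written the offset is nearly complete at 5 years; at 20 and 40 years it is only partial.

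**Step 4: effect of a one-year lead-in.** Excluding both events and person-time in the first year multiplies the excess by exp(-(1/lag + 1/D)).

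- D = 20, f = 25%, lag 0.5: 0.465 x exp(-2.05) = 0.06, so 1.47 falls to 1.06.
- D = 20, f = 25%, lag 2: q = 0.5/0.65 = 0.769, excess 0.385 x exp(-0.55) = 0.22, so 1.38 falls to 1.22.
- D = 40, f = 50%, lag 0.5: 1.882 x exp(-2.025) = 0.25, so 2.88 falls to 1.25.
- D = 40, f = 50%, lag 2: q = 0.5/0.625 = 0.8, excess 1.6 x exp(-0.525) = 0.95, so 2.60 falls to 1.95.

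**Step 5: age cohorts.** Take a childhood diagnosis made before registration and first coded in adulthood. It leaves the paediatric direct numerator. Paediatric incidence is unchanged, since the true date precedes observation. It then enters both adult incidence and adult direct prevalence. The comparison is affected in both cohorts.

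**The case against.** The protocol has real safeguards. It uses history from before registration, and it names inherited disease as an example of what a GP may enter, which points to a lower f in the diseases where the effect could be largest. Section 10 plans a look at age at diagnosis before the cohorts are fixed and mentions excluding unrealistic ages, which could catch some false adult-onset records. Section 11 already admits bias in incidence and duration. These points bear on the size of the problem. None of the planned checks looks at time since registration, and steady turnover would leave the calendar-year incidence plot flat. The checklist marks sensitivity analyses (item 10.8) as not applicable.

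A reader might infer more than the documents support:

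- **That Section 11 declares all date errors harmless.** The nearest antecedent of its closing sentence is the paediatric/adult misclassification, and the text just before concedes bias from wrong dates. On that narrow reading the sentence is harmless for the all-ages cohort, but still wrong for the age cohorts (step 5).
- **That a patient who moves repeatedly is counted repeatedly.** The documents do not say how persons are identified across practices, and Table 4 allows one entry. The calculation needs only existing cases arriving, not the same person counted twice.
- **That direct prevalence is untouched.** Slow coding lowers it somewhat, and the age cohorts exchange cases.
- **That the inflation factors estimate the bias in these databases.** They rest wholly on assumed inputs. Where the median is not reached there is no indirect estimate, although the reported incidence is still affected.

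**Conclusion.** The point holds for Sections 8.3, Table 4 and 8.8.4 as written: unrecorded existing disease is counted as incident. The direction is firm, since incidence rose in every scenario with missing history while all-ages direct prevalence moved little. The size is not known from the documents. For 10-50% of histories not entered, 10-year mean registration and a half-year lag, inflation is about 1-3% at 1 year mean duration, roughly x1.2-1.9 at 20 years and x1.4-2.9 at 40 years. At these longer durations the shorter D offsets it only in part. The closing sentence of the Section 11 passage on misdated diagnoses is ambiguous; it is incorrect if read broadly and, for the age cohorts, also if read narrowly. The change is worth making because it is cheap and bears on the study's one objective.

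**What to change.** 1. In 8.3, Table 4 and 8.8.4, start time at risk and count events only after 365 days of prior observation. Exempt persons whose observation starts in the first year of life, so that diagnoses made in infancy are kept.
2. Report the rate without the lead-in alongside. A plot of incidence by time since registration would be a useful optional addition.
3. State that the lead-in reduces the bias without removing it, and that it leaves misdated diagnoses in D.
4. In Section 11, replace the closing sentence of the passage on misdated diagnoses with a statement that such diagnoses bias I and D, have little effect on all-ages direct prevalence, and shift cases between the paediatric and adult cohorts, so that they can affect the comparison. The prevalence population needs no restriction.

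Cost: a cohort setting with one exemption, a second incidence run and a few sentences. Some person-time is lost (with 10-year mean registration, about 1 - exp(-0.1) = 9.5% before the exemption), as are a few true cases diagnosed in the first year after registration.

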6. RATIONALE AND BACKGROUND

Prevalence of a disease or condition is defined as the proportion of individuals in a population affected by a condition at a given point in time. Quantifying disease prevalence is important from a public health perspective, e.g. to understand the impact of diseases on the population, or to plan and allocate health care resources. Measuring disease prevalence is also important from a medicine regulatory viewpoint, as regulatory agencies grant incentives for the development of new therapies for rare diseases, diseases with low prevalence.

If the number of people with the disease is known in a population of known size, direct estimation of the prevalence proportion is straightforward. This holds for a sample of the population, provided the sample is representative of the population. For chronic diseases, complete prevalence, i.e. counting all individuals ever diagnosed with the disease, is typically of interest.

Disease prevalence depends on the rate of incidence of the disease in the population as well as on the average duration of the disease. Under the assumption that both the incidence of the disease and its average duration are stable over time, a well-known mathematical relationship between prevalence (P), incidence (I) and average duration (D) is[1]:

$$\frac{P}{1-P} = I \cdot D$$

For diseases with relatively low prevalence, $(1 - P) \approx 1$ and the above expression reduces to:

 $P = I \cdot D$

Application of this formula can be useful for example when the prevalence is unknown but where the incidence can be estimated from diagnoses in hospitals, and using assumptions for the duration of disease [2], or where input from different sources is combined [3].

This expression can be used to obtain an indirect estimation of disease prevalence from estimates of the disease incidence and mean (or median) duration, provided the following assumptions hold:

- The prevalence is relatively low
- Disease incidence is stable over time
- Disease duration is stable over time

For chronic diseases without cure, the value of D used can correspond to the median survival time after diagnosis. For non-chronic diseases, the value of D used can correspond to the median time from diagnosis to cure.

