In recent years, real-world data (RWD) sources, particularly from primary care, have been used to estimate the prevalence of chronic diseases. The rationale behind this is that the population included in these databases can be considered a representative sample of the general population. The same reasoning has been used to produce incidence figures as well as estimations of disease duration (e.g. survival) using this type of sources.

There is uncertainty however around how direct and indirect methods to estimate prevalence agree with each other, both in situations where the assumptions underpinning the indirect method hold, the degree to which a chronic disease is truly life-long, as well as in settings where they can be more questionable (e.g. because incidence and or disease duration evolved over time). This study aims at addressing this question in the context of using RWD sources.

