8.8.5. Median disease duration

Survival time will be analysed with the R package *survival*. Time zero for the survival analysis is the date of first diagnosis. Patients for whom no date of death is recorded will be censored at the date of end of their observation period or administratively censored at the end of study period.

Median survival time, i.e. disease duration, will be estimated with 95% CI using Brookmeyer-Crowley method [4].

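### Stable disease duration is a stated condition for P = I × D, but only incidence has a planned check over calendar time, and D is one median pooled over all diagnosis years

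*Protocol*

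**What the plan says.** Section 6 allows P = I × D under three conditions. One is low prevalence; the other two are "Disease incidence is stable over time" and "Disease duration is stable over time". The same section says that agreement between the methods is uncertain both where the conditions hold and where they are doubtful, for example "because incidence and or disease duration evolved over time".

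For incidence, section 8.8.4 plans a calendar-year plot, "The incidence rate by calendar year will be plotted to check stability over time", and gives it a purpose: "This will be used in the discussion about the validity of the indirect estimated prevalence".

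For duration, section 8.4 states: "For disease duration, all patients with the diagnosis of interest will be included, without any exclusion criteria". Table 5 adds: "Earliest recording of disease diagnosis will be identified, this can be before or during observation time". Section 8.8.5 fixes the clock, "Time zero for the survival analysis is the date of first diagnosis", and follow-up ends at the latest on 31/12/2022 (section 8.3, Table 4). Section 8.8.6 multiplies the overall incidence by the resulting single median. The direct comparator is the point prevalence on 01/01/2016 (section 8.8.3).

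**The concern.** Of the three conditions, low prevalence can be read off the direct estimates and stable incidence has its own plot. Stable duration is the only one left without a check. No section splits or plots survival by calendar time. The preliminary diagnostics in section 10 look at survival time among those who die, not by period, and serve to settle the cohort definitions. Item 10.8 of the checklist in Appendix II, on sensitivity analyses, is marked not applicable.

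D also mixes eras. It can include patients diagnosed long before 2010 and patients diagnosed up to seven years after the comparison date, while I covers 2010-2022 and the direct prevalence refers to one day in 2016.

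What is at stake is the interpretation of the main result. If survival changed while incidence stayed flat, the planned check would pass and the indirect/direct ratio would still shift. The report could not readily say whether a disagreement came from the trend or from the method, or whether an apparent agreement came from two errors cancelling.

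**Working it through.** The protocol gives no figure to reproduce here: no sample size, event count or expected duration. The check is therefore an illustration on assumed inputs.

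**Inputs from the protocol.** Study period 2010-2022; direct prevalence on 01/01/2016; D is the Kaplan-Meier median from first diagnosis in all diagnosed patients, censored at the end of 2022; indirect prevalence is I × D.

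**Assumptions, not from the protocol.** Constant incidence I; exponential survival; full diagnosis history; patients alive in or after 2010 make up the all-patient pool; negligible sampling error. Mean duration is 5 years throughout (stable case), or 5 years for diagnoses before 2013 and 10 years from 2013 (trend case).

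**Step 1, direct prevalence per unit I, trend case.**
- Diagnosed 2013-2015 and alive on 01/01/2016: 10(1 − e^(−0.3)) = 2.59
- Diagnosed before 2013 and alive on that date: 5e^(−0.6) = 2.74
- Total: 2.59 + 2.74 ≈ 5.34. In the stable case it is 5.00.

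**Step 2, the protocol's D and the resulting ratio (simulated).**

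| Pooling for D | Stable: I×D / P | Trend: D | Trend: I×D / P | Relative shift |
|---|---|---|---|---|
| All patients (closest to the protocol) | 0.96 | about 6.55 y | 6.55/5.34 ≈ 1.23 | 1.23/0.96 ≈ 1.28 |
| Diagnoses 2010-2022 only | 0.69 | about 5.56 y | 5.56/5.34 ≈ 1.04 | 1.04/0.69 ≈ 1.51 |

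Repeat runs vary in the second decimal (1.22 to 1.23, and 1.04 to 1.05). The stable ratios are not 1 even without a trend. For exponential survival the median is ln 2 = 0.69 of the mean, which explains the second row. In the first row, counting time from diagnosis for patients who had to survive to 2010 lengthens D and roughly offsets that. In the second row the trend turns a ratio of 0.69 into apparent agreement, which is the masking case.

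**Step 3, other trends.** With baseline means of 3 or 6 years, and either a change of −5% to +5% per diagnosis year from 2000 or a step of ×0.67, ×1.5 or ×2 at 2014, the ratio ranges from 0.70 to 1.30 times its stable value under all-patient pooling. With 2010-2022 diagnoses only, it ranges from 0.63 to 1.59 times. Incidence is exactly flat in every scenario, so the planned plot shows nothing.

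**Step 4, would a period split show it?** With delayed entry at the window start, the medians for 2010-2015 and 2016-2022 are 3.45 and 3.48 years in the stable case (theory: 5 × ln 2 = 3.47). In the trend case they are about 3.86 and 6.38 years. The 2010-2015 ratio against 01/01/2016 is then 3.86/5.34 ≈ 0.72, close to the stable 0.69: most of the trend effect is gone and the median-versus-mean gap remains.

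**The case against.** The strongest counter-argument is that the planned plots already hold the information. Section 8.8.3 reports prevalence on 1 January of every year. Flat incidence with moving prevalence points to changing duration. In the trend case, prevalence per unit I rises from 5.00 in 2013 to 10(1 − e^(−0.9)) + 5e^(−1.8) = 5.93 + 0.83 = 6.76 in 2022, about 35%. This stands as mitigation. But the protocol assigns that series only to describing trends, and rising prevalence could also reflect better recording of past diagnoses, so it does not replace a look at survival itself.

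A second argument is that splitting a survival curve by period belongs in an analysis plan. That carries limited weight, because the protocol itself specifies the incidence check and the formulas for D.

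A third concerns the remedy. In the illustration, the 2010-2015 ratio of 0.72 lies further from 1 than the pooled 1.2. That is true, but its use is to separate the trend from the median-versus-mean gap, not to bring the ratio to 1. Fewer deaths per window is a real cost, and section 8.9 already expects that some medians will not be observed.

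Three stronger readings are tempting, and the protocol does not support them:
- A reader might infer that a trend would be declared a failure of the indirect method. The protocol tests no hypothesis and sets no rule for agreement or failure.
- A reader might infer that the study undertakes to sort diseases into those that meet the conditions and those that do not. Section 7 sets only a comparison as the objective; section 6 describes uncertainty in both settings.
- A reader might size the effect with mean durations: for 2010-2022 diagnoses, (3/13) × 5 + (10/13) × 10 = 8.85, and 8.85/5.34 = 1.66. The arithmetic is right, but the protocol uses a censored Kaplan-Meier median in all patients, for which the ratio is about 1.2.

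**Conclusion.** The gap is real and modest. Stable duration is a stated condition and part of the motivating question, yet it has no planned check over calendar time, and the pooled D is not aligned in time with the comparison date. Under the assumed doubling of mean duration from 2013, the ratio under the protocol's own pooling moves by a little over a quarter (0.96 to about 1.2). Across the other scenarios it moves by up to about 30% either way. These sizes rest on exponential survival, full diagnosis history and invented trends; they show what could happen, not what will happen in these five diseases. The planned estimates can still be produced, and the yearly prevalence series gives a partial hint. This is a cheap improvement, not a flaw that invalidates the comparison.

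**What to change.** In section 8.8.5, add descriptive survival for two calendar periods, 2010-2015 and 2016-2022. Patients diagnosed before a window enter the risk set at the window start (or at the start of their observation period, if later), and follow-up is censored at the window end. Report the median with its interval or, where the median is not reached, survival at one fixed time named in advance.

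Show the two curves beside the annual incidence and prevalence plots, and add them to the validity discussion named in section 8.8.4. Report I × D from 2010-2015 as a sensitivity comparison with the 01/01/2016 prevalence, noting that the median-versus-mean gap remains in it. Keep the pooled D as the main result. A formal stable/not-stable label is not needed without a criterion to support it.

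The cost is two more survival fits per cohort: at most 5 diseases × 3 age cohorts × 3 databases × 2 = 90 runs of the same code. The downside is fewer deaths and wider intervals per window, and some small cohorts will fall under the minimum count.
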